4.7. Interim Analyses

The purpose of the interim analysis is to present results of the analysis for the primary outcome of the long-term safety of Nucala, the secondary outcomes of the long-term effectiveness of Nucala, and the exploratory outcomes using dataset including data until 48 weeks post-exposure. This analysis does not lead to a decision to amend the design or to stop the study.

4.8. Changes to Protocol Defined Analyses

There were no changes or deviations to the originally planned statistical analysis specified in the protocol amendment 01 (Dated: 27-JUL-2020).

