#### 4.5. Primary Analysis

The primary analysis will be based on the TP population. Adverse events will be coded using the Medical Dictionary for Regulatory Activities (MedDRA) and summarized by preferred terms. All AEs, SAEs, ADRs and AESIs will be summarized separately. Exposure-adjusted AE rate for these AE will also be summarized.

The summary table will be also produced by the observation period, the follow-up period and the total period (the observation period and the follow-up period), respectively.

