# 4.6. Secondary and Exploratory Analyses

The secondary and exploratory analyses will be performed for the TP population. All endpoints will be summarised by using appropriate descriptive statistics.

The summary table will be also produced by the observation period and the follow-up period, respectively.

The endpoints selected for secondary and exploratory analyses are listed below by objective:

To investigate the long-term effectiveness of Nucala in adult patients with EGPA in Japan

- Proportion of participants with clinical symptoms as assessed by 9 organ-systems (i.e. systemic, skin, mucous membranes/eyes, ears/nose/throat, chest, cardiovascular, abdominal, renal, nervous system) for the observation period of 96 weeks.
- Proportion of participants with EGPA relapse for the observation period of 96 weeks.
   EGPA relapse is defined as any of the following with worsening EGPA.\*
  - 1) Increased dose of OCS.
  - 2) Initiation/increased dose of immuno-suppressive agents.\*\*
  - 3) EGPA treatment with hospitalization.
  - \* Worsening of EGPA: new onset of EGPA symptoms or worsening of existing symptoms.
  - \*\* Immunosuppressive agents: If the dose of immunosuppressive agents increases for the same formulation or if the number of immunosuppressive agents increases for EGPA treatment.
- Annualized rate (event/year) of hospitalization for EGPA-related events

213684

 Annualized rate (event/year) of emergency room/unscheduled visit for EGPA-related events

The annualized rate of hospitalization for EGPA treatment will be analysed by using a negative binomial generalized linear model with logarithm of time as an offset variable, from which the estimated event per year and associated 95% CIs will be calculated.

- Average daily dose (prednisolone-equivalent) of OCS over 96 weeks
- The proportion of subjects in the dosing categories\* relative to average daily OCS (prednisolone-equivalent) over 96 weeks
  - \* Zero, >0 to ≤4.0 mg/day, >4.0 to ≤7.5 mg/day, >7.5 mg/day

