#### To investigate the condition of complicated asthma

• Annualized rate (event/year) of asthma exacerbation.

The annualized rate of asthma exacerbation will be analysed by using a negative binomial generalized linear model with logarithm of time as an offset variable, from which the estimated event per year and associated 95% CIs will be calculated.

To explore the effect on pulmonary function

To explore the effect on the cardiac function

The statistical model was selected with reference to previous clinical studies of Nucala. However, for a model checking and diagnostics, the fit of the negative binomial generalized linear model will be investigated by calculating standardized deviance residuals and plotting these on a "Q-Q" plot with simulation-generated tolerance boundaries, where appropriate.

Further details of the secondary and exploratory analyses including covariates will be provided in the RAP or the supplementary RAP, when needed.

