# 4.7. Subgroup Analysis

The following subgroups are of interest in this study. A separate exploratory analysis of the prespecified endpoints within each subgroup will be carried out. Subgroup categories may be further collapsed if there are a small number of participants within a subgroup.

The following subgroups are of interest:

- Sex
- Age
- Duration of EGPA disease
- Severity of EGPA disease
- Adherence to recommended treatment regimen for Nucala
- Current medical conditions (e.g., presence/absence of asthma, allergic rhinitis, etc.)
- Medical history (e.g., presence/absence of asthma, allergic rhinitis, etc.)
- Prior use of Nucala for asthma

- Previous therapeutic regimen for EGPA disease (e.g., presence/absence of plasma exchange therapy, operation, etc.)
- Prior use of other biological medications
- ANCA
- Favourable treatment response with Nucala
- Immuno-suppressive therapy
- EGPA disease relapse
- Clinical symptoms
- COVID-19 infection

Further details of the subgroup analyses will be provided in the RAP.

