SAP Version	Approval Date Protocol Version (Date) on which SAP is Based		Change	Rationale
1.0	8 Apr 2022	Amendment 01	Not Applicable	Original version
2.0	15 Jun 2022	Amendment 01	Section 4.3.1.2: Added calculation of annualized rate for retrospective period. Clarified definition of total duration of OCS administration. Added derivation method of eosinophil count. Section 6.2.2 or Section6.2.4: Corrected the ambiguous wording of "first dose of Nucala". Section 6.2.2: Added the definition of observation period for missing case.	Clarifications and additional considerations were required for valid analyses.
3.0	12 Dec 2022	Amendment 01	Added summaries for: - ANCA+/- - EGPA remission - Immuno-suppressive therapy - Asthma exacerbation - Average daily dose of OCS - Annualized rate of hospitalization for EGPA- related events - Annualized rate of ER/unscheduled visit for EGPA-related events	Clarifications and additional considerations were required for valid analyses.
4.0	18 Apr 2023	Amendment 01	"Active + worsening" category was added for the summaries of clinical	Clarifications and additional considerations

SAP Version	Approval Date	Protocol Version (Date) on which SAP is Based	Change	Rationale
			symptoms as assessed by 9 organ-systems Analysis of Annualized Rate (event/year) of Asthma Exacerbation for each of the 3 categories is added The definition of follow-up is changed The definition and the assessment point of EGPA relapse is changed A line plot is added for OCS	were required for valid analyses.
5.0	17 May 2023	Amendment 01	The duration between the start of retrospective period to the end of observation period summary were added The definition of the observation period and the follow-up period is changed	They are considered imperative to evaluate the safety of Nucala. The definition is aligned with the standard exposure definition of

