The summary be provided for AESI. The percentage will be calculated in two ways; one with number of participants with event as the denominator and the other with total number of participants as the denominator. The worst-case approach will be applied at participant level for the maximum intensity (i.e. a participant will only be counted once as the worst case from all the events experienced by the participant). For action taken to an event, a participant will be counted once under each action (e.g. if a participant has an event leading to both study discontinuation and dose reduction, the participants will be counted once under once under both actions).

Listings of all AEs and of subject numbers for individual AEs will be displayed. Reasons for considering as a SAE, AEs leading to withdrawal from study and AESIs will also be listed. In addition, patient profiles will be provided of patients with deaths.

Exposure-adjusted AE rate (the number of events per 1000 participant-years of exposure) for the AEs will also be summarized. This summary table will be produced by the

observation period and the total period (the observation period and the follow-up period), respectively.

The number of events per 1000 participant-years of exposure will be calculated as:

 $(1000 \times \text{number of AEs during the period}) / (total duration of exposure in days / 365.25)$

The derivation of the total duration of exposure in days is defined in 6.2.3.

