4.3. Secondary Endpoint(s) Analyses

4.3.1. Secondary endpoint(s)

4.3.1.1. Definition of endpoint(s)

The secondary endpoints are as follows:

- Proportion of participants with clinical symptoms as assessed by 9 organ-systems (i.e. systemic, skin, mucous membranes/eyes, ears/nose/throat, chest, cardiovascular, abdominal, renal, nervous system)
- Proportion of participants with EGPA relapse
- Annualized rate (event/year) of hospitalization for EGPA-related events
- Annualized rate (event/year) of emergency room/unscheduled visit for EGPA-related events
- Average daily dose (prednisolone-equivalent) of oral corticosteroid (OCS) over the observation period
- The proportion of participants in the dosing categories^{*} relative to average daily OCS (prednisolone-equivalent) over the observation period
 * 0 mg/day, 0 mg/day < ≤ 4.0 mg/day, 4.0 mg/day < ≤ 7.5 mg/day, 7.5 mg/day <

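### SAP 4.8 reports no departure from the protocol's analyses, but 11 of 16 subgroups and the follow-up-period AE tables are missing and the OCS averaging period is inconsistent

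*SAP*

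**What the plan says.** SAP 4.8 is a single sentence: "There were no changes or deviations to the originally planned statistical analysis specified in the protocol amendment 01".

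The protocol text it has to match is as follows.

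- **Subgroups.** Protocol 4.7 says "A separate exploratory analysis of the prespecified endpoints within each subgroup will be carried out" and then lists 16 subgroups. It allows small categories to be collapsed and leaves further details to the analysis plan.
- **AE periods.** Protocol 4.5 asks for AE summaries for the observation period, the follow-up period and the two combined. On rates it says "Exposure-adjusted AE rate for these AE will also be summarized", just after naming AEs, SAEs, ADRs and AESIs.
- **OCS.** Protocol 4.6 lists "Average daily dose (prednisolone-equivalent) of OCS over 96 weeks".

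The SAP's counterparts are these.

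- SAP 4.6.4 lists six subgroups. Its closing remark leaves room for more but names none.
- SAP 4.2.2 gives AE summaries for the observation and total periods. The exposure-adjusted rate "for the AEs will also be summarized", for the same two periods.
- SAP 4.3.1.1 defines "Average daily dose (prednisolone-equivalent) of oral corticosteroid (OCS) over the observation period". SAP 1.1 still gives the endpoint over 96 weeks.

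**The concern.** The study is descriptive, with no hypothesis tests, so its credibility rests on readers being able to see what was planned and what changed. SAP 1 says the document sets out the analyses for the Clinical Study Report, so an inaccurate conformity statement could be carried into that report.

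The departures also touch the primary objective, which is long-term safety. AE frequency by age and sex would not be tabulated, and neither would AEs arising after Nucala has been stopped for more than 28 days. For OCS, a secondary endpoint, two definitions stand in the same SAP, and they can place a participant who stops early in different dosing categories.

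**Working it through.** The plan gives no figure on this point, so the check is mainly an item-by-item comparison, with one arithmetic illustration.

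**1. Subgroups (Protocol 4.7 against SAP 4.6.4).**

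| Status in SAP | Subgroups | Count |
|---|---|---|
| Kept as named | severity, ANCA, immunosuppressive therapy, relapse | 4 |
| Recast | disease duration, now time from diagnosis to Nucala | 1 |
| No endpoint analysis | sex, age, adherence, current conditions, medical history, earlier Nucala for asthma, earlier EGPA regimen, earlier biologics, favourable response, clinical symptoms, COVID-19 | 11 |
| New | average OCS dose | 1 |

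16 − (4 + 1) = 11 absent. If the recast item is counted as not kept, 16 − 4 = 12. Clinical-symptom status does appear in SAP 4.6.4, but only to split baseline characteristics. SAP 6.1.2 already defines sex and the age cut at 65 years, so both can be tabulated.

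**2. AE periods (Protocol 4.5 against SAP 4.2.2).** Three periods become two, for frequencies and for exposure-adjusted rates. For any AE term, let O, F and T be the numbers of participants with an event in the observation, follow-up and total periods, and B the number with events in both. Then

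T = O + F − B, so F = T − O + B.

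The SAP tables give T and O but not B. F is therefore known only to be at least T − O. Event counts can be subtracted; participant counts cannot.

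**3. OCS period (Protocol 4.6 and SAP 1.1 against SAP 4.3.1.1).** SAP 6.2.2 ends the observation period 28 days after Nucala stops. For a participant treated to Week 96 the two periods essentially agree. For an early stopper they do not. As an illustration with assumed doses, take OCS at *a* = 4 mg/day until the observation period ends and *b* = 8 to 10 mg/day from then to Week 96. With Nucala stopped at week *k*, the 96-week average is

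[a(k + 4) + b(96 − k − 4)] / 96.

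| Nucala stop | Observation-period average | 96-week average, b = 8 | 96-week average, b = 10 |
|---|---|---|---|
| Week 24 | 4.0 | (112 + 544)/96 = 6.83 | (112 + 680)/96 = 8.25 |
| Week 48 | 4.0 | (208 + 352)/96 = 5.83 | (208 + 440)/96 = 6.75 |
| Week 72 | 4.0 | (304 + 160)/96 = 4.83 | (304 + 200)/96 = 5.25 |

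In every row the participant leaves the category above 0 and up to 4.0 mg/day. In one cell (8.25) the average passes 7.5 mg/day. In addition, SAP 4.3.1.2.5 derives the whole-period average, but the summaries it specifies are for the retrospective period and the 12-weekly windows only.

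**The case against.** The best defence is that the protocol calls the subgroup work exploratory, defers its details to the analysis plan and allows categories to be merged, and that SAP 4.6.4 leaves room for further subgroups. This shows that the omission may not be permanent. It does not support 4.8: latitude to detail and merge is not latitude to remove without saying so, and the closing remark in 4.6.4 commits to no particular subgroup. The protocol does not rank its subgroups, so giving priority to age and sex is a judgement based on the safety objective.

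On OCS, Protocol 4.6 itself speaks of a 96-week observation period and asks for summaries by period. That is a fair point. The problem is best described as an inconsistency inside the SAP, with effect only for early stoppers, and not as a deliberate change of endpoint.

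Several stronger readings are tempting, and the documents do not support them.

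- **Safety results are lost.** All AEs remain in the total-period tables and listings, and AEs of participants with COVID-19 are listed (SAP 4.5.2.1).
- **Relapse was redefined after an interim look at the data.** The version history does say "The definition and the assessment point of EGPA relapse is changed", but that compares SAP versions. The current definition in SAP 4.3.1.2.2 has the same three components as Protocol 4.6 and essentially the same notes. The earlier derivation is not shown, and no interim lock date is given. Blinding has no role in a single-arm study whose interim analysis leads to no decision. No relapse sensitivity analysis follows from this.
- **The model check was abandoned.** Protocol 4.6 says "the fit of the negative binomial generalized linear model will be investigated by calculating standardized deviance residuals", but only where appropriate. The check is absent from the visible hospitalization and ER/unscheduled-visit sections (SAP 4.3.1.2.3 and 4.3.1.2.4). It could sit in SAP 4.4, which is redacted.
- **Exposure-adjusted rates were cut to one event class.** The SAP wording is ambiguous, because its section covers all four classes. Only the loss of the follow-up period is certain.

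**Conclusion.** The conformity statement in SAP 4.8 is inaccurate. Two departures are certain from the visible text: 11 of 16 protocol subgroups have no endpoint analysis, and AE reporting falls from three periods to two. The third point, the OCS period, is a contradiction between SAP 1.1 and SAP 4.3.1.1. It can move early stoppers between dosing categories, but the size of that effect depends on how many stop and on their later doses, which the documents do not give. The averages shown rest on assumed doses.

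The consequence is moderate: a documentation error, together with missing descriptive tables that bear on the primary safety objective. The model check and the event classes for the rates need confirming and are not established departures. Whether the final report will repeat the sentence cannot be known from these documents.

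**What to change.** - **SAP 4.6.4:** restore AE frequency by sex and by age (under 65, 65 and over), using the categories in SAP 6.1.2.
- **SAP 4.2.2:** restore the follow-up-period AE tables, and state that exposure-adjusted rates cover AEs, SAEs, ADRs and AESIs. The exposure formula in SAP 6.2.3 (stop − start + 29 days) counts no later off-drug time, so a denominator must be stated for any rate that includes follow-up events.
- **SAP 1.1 and 4.3.1.1:** make the OCS period the same in both and report the 96-week average as the protocol states. Say how participants who leave the study before Week 96 are handled.
- **SAP 4.3.1.2.3 and 4.3.1.2.4:** if the redacted SAP 4.4 does not contain the residual Q-Q check, add it for these two models.
- **SAP 4.8:** replace the sentence with a list of the remaining departures, including the subgroups not restored and the added OCS subgroup, with a reason for each.

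This needs SAP wording and some extra tables from data already collected. The downside is somewhat longer output, and the restored tables will have small counts and should be read descriptively.

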5. SAMPLE SIZE DETERMINATION

In a global Phase 3 study (MIRRA study) [Wechsler, 2017] conducted in EGPA patients (mepolizumab group: 68 patients), the minimum frequency of AEs was 1.47% (1/68 patients). Assuming a binominal distribution, 107 participants are required to detect at least one case of an AE occurring with the frequency of 1.5% or higher with the probability of 80%. With an expected dropout rate of 10%, a total of approximately 120 participants are needed as the safety analysis population.

A total of 80 and 153 participants are required to detect at least one case of an AE occurring with the frequency of 1.5% or higher with the probabilities of 70% and 90%, respectively.

No sample size re-estimation is planned.

6. SUPPORTING DOCUMENTATION

6.1. Appendix 1 Study Population Analyses

The study population analyses will be based on the All Subjects Enrolled (ASE) population or Treated Population (TP), unless otherwise stated.

6.1.1. Participant Disposition

A summary of the number and percentage of participants who completed the study as well as those who prematurely withdrew from the study and screening failure will be provided. Reasons for study withdrawal and screening failure will also be summarized and listed. Those who have discontinued Nucala treatment but not withdrawn from study will be categorized as study completion. Screen failure summary will be based on the screened population.

The number and percentage of participants who completed Nucala treatment as well as the number who discontinued Nucala treatment prior to the end of the study will be summarized, along with the reasons for discontinuation of Nucala treatment, and these will also be listed for the TP population.

The number and percentage of participants who entered in the observation period and in the follow-up period will be summarized. Participants who have discontinued the treatment of Nucala on or after the first treatment discontinuation +29 days are defined as the participants in the follow-up period.

Туре	Definitions
Study completion	A participant completed the observation period, which is scheduled for 96 weeks (approximately 2 years) at maximum.
Early withdrawal	A participant who was enrolled to this study but withdrew during the observation period.
Screening failure	A participant who consented to participate in the study but did not meet the eligibility criteria at Screening.

Study completion, early withdrawal and screening failure are defined as follows.

6.1.2. Demographic and Baseline Characteristics

The demographic and baseline characteristics will be summarized with descriptive statistics and listed based on the TP.

Demographic and baseline characteristics	Detail
Sex	Male
	Female

Demographic and baseline characteristics	Detail
Age (year)	1) Continuous 2) $< 15, 15 \le < 65, 65 \le < 75, 75$ \le 3) $< 65, 65 \le$
Height (cm)	Continuous
Weight (kg)	 Continuous ≤ 70, 70 < ≤ 85, 85 <
BMI (kg/m ²) BMI (kg/m ²) = weight (kg) / [height (m)] ²	Continuous
Severity of EGPA disease Defined by Japan Intractable Diseases Information Center (Japan Intractable Diseases Research Foundation)	1, 2, 3, 4, 5
Duration of EGPA disease (year)	 Continuous ≤ 2, 2 < ≤ 5, 5 < ≤ 10, 10 <
Medical conditions	Yes No
Concomitant medications	Yes No
Clinical symptoms (9 organ-systems) i.e. systemic, skin, mucous membranes/eyes, ears/nose/throat, chest, cardiovascular, abdominal, renal, nervous system	Yes No by 9 organ-systems
Hospitalization for EGPA-related events during the Retrospective period	Yes No
ER/Unscheduled visit for EGPA-related events during the Retrospective period	Yes No
Asthma exacerbation during the Retrospective period	Yes No
Clinical laboratory parameters: haematological parameters test	Continuous
	Continuous

6.1.3. Protocol Deviations

No per protocol analysis is planned for this study.

Important protocol deviations will be summarized and listed for the ASE. A listing of subjects with inclusion/exclusion criteria deviations will also be provided.

Protocol deviations will be tracked by the study team throughout the conduct of the study in accordance with the Protocol Deviation Management Plan (PDMP), which is specifically developed for this study.

Data will be reviewed prior to DBL (database lock) to ensure all deviations are captured and categorized in the protocol deviations AR dataset.

The deviations dataset will be the basis for these summaries and listings.

The visits impacted by COVID-19 will be summarized and listed for the ASE.

6.1.4. Medical Conditions and Concomitant Medications

Current medical conditions are defined as currently occurring diseases at screening. Past medical conditions are defined as diseases not occurring at screening but in the past. Medical conditions will be summarized by current and past for the ASE.

Concomitant medications (other products, corticosteroid, immunosuppressants, and immunoglobulin) will be coded using the GSK Drug. The summary of concomitant medications will be provided by ingredient (i.e. multi-ingredient medications will be summarized for each individual ingredient rather than a combination of ingredients). The summary will be created using ingredient base names (i.e. ingredients with the same base name but different salt will appear under one base name in the summary). Anatomical Therapeutic Chemical (ATC) classifications will not appear in the summary.

Summaries of concomitant medications will be provided for the observation period, the follow-up period and the retrospective period. Concomitant medications will also be listed by ingredient. They will be displayed for the ASE.

Classification of a concomitant medication into study phase (at study entry, screening/run-in period, stabilization period, on-treatment, post-treatment, or post-study) will be made with reference to the study phase as defined above. A medication will be classified into every period in which it was taken. For medications with partial start and stop dates, the medication will be classified into every period in which it could have been taken.

